8.2 SELECTION OF STUDY POPULATION

At Pre-screening Visit, all patients will sign the informed consent to perform CD205 IHC analysis on the most recent archived FFPE tissue samples. The percentage of CD205 positive cells and level of expression 1+, 2+, 3+ will be collected.

Pre-screening Period can be extended for patients with CD205-positive solid tumors and NHL until they proceed to the Screening Visit.

NOTE: If the archived tissue has resulted negative for CD205 at IHC analysis, CD205 positivity can be reassessed if a new biopsy becomes available upon collection of new Pre-screening consent. Patients will be pre-screened based on CD205 positive solid tumors or CD205 positive NHL. Eligibility of patients to the study will be checked at Screening Visit and re-checked at Visit 1. Patients will be included only if they meet all of the patient inclusion criteria (§8.2.1) do not meet any of the exclusion criteria (§8.2.2).

8.2.1 Inclusion criteria

Patients meeting all the following criteria will be eligible for entry into the study:

1. Male or female patients aged ≥ 18 years.
2. For Step 1 of the study, patients with confirmed diagnosis of a solid tumor will be included based on the following characteristics:
 - Histological confirmed locally advanced or metastatic solid tumor, progressive after last treatment received and for which no standard curative therapy is available or the patient refuses standard therapy. For the purpose of this study, progressive disease is defined by RECIST v1.1.
 - Measurable or evaluable disease by Response Evaluation Criteria in Solid Tumors guideline (RECIST v1.1).
 - Availability of archived tumor material, either as a block or slides, which are locally assessed during the Pre-screening Period through immunohistochemistry (IHC) and show positivity ($\geq 1+$ IHC staining) for CD205. A new biopsy will be performed whenever possible upon patient's consent, during the screening period, if the archived tumor material is older than 3 months.
3. For Step 2 of the study, patients with NHL will be included based on the following characteristics:
 - Histological confirmed diagnosis of multiple relapsed or refractory NHL. Patient requires treatment because of NHL relapse following response to standard chemotherapy or high-dose chemotherapy + stem cell transplantation (SCT), or NHL is refractory [i.e., failure to achieve at least complete response (CR), partial response (PR) or stable disease (SD)] to its more

recent chemotherapy. Patient refuses standard therapy and is not eligible for autologous SCT (ASCT).

- Measurable or evaluable disease by Cheson Criteria (The Lugano Classification, 2014).
- CD205 positive NHL, locally assessed through IHC testing on the most recent archived tumor sample ($\geq 1+$ IHC staining) during the Pre-screening Period. A new biopsy will be performed whenever possible upon patient's consent, during the screening period, if the archived tumor material is older than 3 months.

4. Patients must be willing to receive transfusions of blood products.

5. Eastern Cooperative Oncology Group (ECOG) performance status (PS) of 0 to 2.

6. Neutrophil count within normal value; platelets $\geq 100,000/\mu\text{L}$; haemoglobin $\geq 9\text{ g/dL}$.

7. Adequate renal and hepatic laboratory assessments:

- creatinine $\leq 1.5\text{ mg/dL}$ or creatinine clearance $> 60\text{ mL/min}$
- bilirubin $\leq 1.5\text{ mg/dL}$
- hepatic transaminases and ALP $\leq 2.5 \times \text{ULN}$ or $\leq 5 \times \text{ULN}$ if hepatic metastases are present; $\leq 5 \times \text{ULN}$ for only ALP if bone metastases are present.

8. Life expectancy of at least 2 months.

9. A Female is eligible to participate if she is not pregnant, not breastfeeding, or at least one of the following conditions applies:

- She is not a woman of childbearing potential (WOCBP) (see Appendix I).
OR
- She is a WOCBP who agrees to use highly effective contraception (see Appendix I) 4 weeks before the first dose of study treatment, during the treatment period, and for 2 months following the last study drug administration.

10. A Male must agree to use and have their female partners using a highly effective method of contraception (see Appendix I) 4 weeks before the first dose of study treatment, during the treatment period, and for 2 months following the last study drug administration.

11. Able to give written informed consent before any study-related procedure.

NOTE: The locally assessed, slides from archived tissue and optional new biopsies, in conjunction with 5 to 20 unstained slides and/or residual FFPE block, will be collected for retrospective central analysis.

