8.2.2 Exclusion criteria

Patients will not be eligible to participate to the study if they meet ANY of the following exclusion criteria:

1. Central nervous system involvement (excluding treated stable cerebral metastasis, not requiring therapy to control symptoms in the last 60 days).
2. Acute infection requiring IV antibiotics, antivirals, or antifungals within 14 days prior to the initiation of treatment (oral treatment are allowed).
3. Grade ≥ 2 peripheral neuropathy.
4. Pregnant or breastfeeding women.
5. Life-threatening illnesses other than solid tumors and NHL, uncontrolled medical conditions or organ system dysfunction which, in the Investigator's opinion, could compromise the patient's safety, or put the study outcomes at risk.
6. Any chemotherapy, radiotherapy, immunotherapy, major surgery, biologic, investigational or hormonal therapy for treatment of solid tumors or lymphoma within 28 days of the first administration of study treatment.
7. Less than 2 previous cancer treatments, including high-dose chemotherapy and ASCT, for NHL unless patient refuses standard therapy and/or is not eligible for ASCT.
8. Known history of human immunodeficiency virus (HIV) or active infection with hepatitis C virus (HCV) or hepatitis B virus (HBV).
9. Have an active or chronic corneal disorder or Sjogren's syndrome.
10. Have any ongoing acute inflammatory skin disease or chronic skin disease not controlled by specific treatment.
11. Have been diagnosed with another primary malignancy, except for: adequately treated non-melanoma skin cancer or cervical cancer in situ; definitively treated non-metastatic prostate cancer; or patients with another primary malignancy who are definitively relapse-free with at least 3 years elapsed since the diagnosis of the other primary malignancy.
12. Have significant, uncontrolled, or active cardiovascular disease, specifically including, but not restricted to:
 - Myocardial infarction (MI) within 6 months prior to the first dose of study drug.
 - Unstable angina within 6 months prior to first dose of study drug.
 - Congestive Heart Failure (CHF) NYHA Class III-IV
 - Diagnosis of short or long QT syndrome.
 - History of clinically significant atrial arrhythmia (including clinically significant bradycardia), as determined by the treating physician.
 - Any history of ventricular arrhythmia.

- Cerebrovascular accident or transient ischemic attack within 6 months prior to first dose of study drug.

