13. APPENDICES

13.1 APPENDIX I: Contraceptive Guidance and Woman of Childbearing Potential

Definitions

Woman of Childbearing Potential (WOCBP)

A woman is considered fertile following menarche and until becoming postmenopausal unless permanently sterile. Permanent sterilization methods include hysterectomy, bilateral salpingectomy, and bilateral oophorectomy.

Women in the following categories are not considered WOCBP

- Premenopausal female with 1 of the following:
 - Documented hysterectomy
 - Documented bilateral salpingectomy
 - Documented bilateral oophorectomy

Note: Documentation can come from the site personnel's: review of participant's medical records, medical examination, or medical history interview.

- Premenarchal
- Postmenopausal female
 - Females who are postmenopausal (age-related amenorrhea \geq 12 consecutive months and increased follicle-stimulating hormone [FSH] $>$ 40 mIU/mL), or who have undergone hysterectomy or bilateral oophorectomy are exempt from pregnancy testing. If necessary to confirm postmenopausal status, an FSH will be drawn at Screening.
 - Females on HRT and whose menopausal status is in doubt will be required to use one of the non-hormonal highly effective contraception methods if they wish to continue their HRT during the study. Otherwise, they must discontinue HRT to allow confirmation of postmenopausal status before study enrollment.

Contraceptive Guidance

| Highly Effective Contraceptive Methods That Are User Dependent | |
|--|--|
| Failure rate of <1% per year when used consistently and correctly ^a . | |
| Combined (estrogen- and progestogen-containing) hormonal contraception associated with inhibition of ovulation ^b : 
▪ Oral▪ Intravaginal▪ Transdermal | Progestogen-only hormonal contraception associated with inhibition of ovulation ^b : 
▪ Oral▪ Injectable |
| Highly Effective Contraceptive Methods That Are User Independent | |

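### Inclusion criterion 9 uses *or* where *and* is needed, so a woman of childbearing potential who uses no contraception is eligible as written

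*Protocol*

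**What the plan says.** Protocol section 8.2.1, criterion 9, opens: "A Female is eligible to participate if she is not pregnant, not breastfeeding, or at least one of the following conditions applies". Two conditions follow, joined by a capitalised OR. The first is that she is not a woman of childbearing potential (WOCBP) as Appendix I defines it. The second begins "She is a WOCBP who agrees to use highly effective contraception (see Appendix I) 4 weeks before the first dose of study treatment" and runs through treatment to two months after the last dose. The synopsis (section 2, Inclusion Criteria) has the same lead-in and the same two conditions.

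Three other places bear on the point:

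- Exclusion criterion 4 (section 8.2.2) reads in full: "Pregnant or breastfeeding women".
- Inclusion criterion 10 sets the rule for men without any alternative: "A Male must agree to use and have their female partners using a highly effective method of contraception".
- Appendix I (section 13.1) defines WOCBP and lists acceptable methods. It imposes a duty of its own on one group: "Females on HRT and whose menopausal status is in doubt will be required to use one of the non-hormonal highly effective contraception methods". A footnote adds a second method where a hormonal contraceptive may interact with the study drug.

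The SAP does not restate the eligibility criteria.

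**The concern.** Taken literally, being neither pregnant nor breastfeeding is enough to satisfy criterion 9, and the contraception condition never decides anything. The criterion then repeats exclusion 4 and adds nothing to it.

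MEN1309 carries DM4, described in section 6.2.1 as a potent microtubule inhibitor, and this is its first use in humans. The footnote in Appendix I ties the two-month period after the last dose to elimination time plus an allowance for genotoxic potential, so the sponsor itself treats pregnancy during exposure as a risk to be prevented. The eligibility rule should carry that protection, and as worded it does not.

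The contrast with criterion 10 shows the gap. The partner of a male patient, who receives no drug, must use contraception. A female patient, who receives the drug, need not. The two criteria cover different people and do not contradict each other, but they differ in strength in the wrong direction.

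**Working it through.** There is no stated figure to reproduce; the check is one of logic.

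**Inputs.** Four yes/no facts about a female candidate: pregnant (P), breastfeeding (B), of childbearing potential (W), agrees to highly effective contraception (C). That gives 2 × 2 × 2 × 2 = 16 combinations. Some are not realistic, such as pregnant but not of childbearing potential, but keeping them does no harm.

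**Rules.**

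- Listed conditions (criterion 9): L = (not W) or (W and C)
- Criterion 9, reading A, with the comma taken as *and*: (not P and not B) or L
- Criterion 9, reading B, with every item an alternative: not P or not B or L
- Exclusion 4: out if P or B
- Corrected criterion 9: not P and not B and L

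**Criterion 9 alone.** L is true in 12 combinations (8 with W = no, 4 with W = yes and C = yes) and false in 4 (W = yes, C = no). Reading A adds the one of those 4 with P = B = no, giving 13 of 16. Reading B adds the three in which P and B are not both yes, giving 15 of 16.

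**Criterion 9 with exclusion 4.** Exclusion 4 removes all 12 combinations with P or B. The other four are:

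| Pregnant | Breastfeeding | WOCBP | Agrees to contraception | Reading A | Reading B | With *and* |
|---|---|---|---|---|---|---|
| no | no | no | no | eligible | eligible | eligible |
| no | no | no | yes | eligible | eligible | eligible |
| no | no | yes | no | **eligible** | **eligible** | **not eligible** |
| no | no | yes | yes | eligible | eligible | eligible |

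Both readings leave the same four eligible. These are exactly the four that exclusion 4 alone would leave, so as written criterion 9 excludes nobody. With *and*, three remain. One combination changes, the WOCBP without contraception, and the other 15 do not.

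**Does other text close the gap?** No other inclusion or exclusion criterion asks female patients for contraception. The duties in Appendix I reach women on HRT whose menopausal status is in doubt and cases of possible hormonal interaction, not every WOCBP. Pregnancy testing at screening, before each cycle and at the End of Study Visit (section 8.5.4.5), withdrawal on pregnancy (section 8.2.3) and pregnancy reporting (section 8.6.5) detect or respond to a pregnancy. They do not require that it be prevented.

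**The case against.** The strongest reply is that this is a slip in one connective and no site would be misled. Exclusion 4 already deals with pregnancy and breastfeeding, so the contraception test is the only work left for criterion 9. The condition sets exact timing, which has no purpose if contraception is optional. Appendix I asks for a second method in some cases, which presupposes a first. The literal *or* would even let a pregnant woman who agrees to contraception meet criterion 9, against exclusion 4. Repeated pregnancy testing limits the consequences, and no endpoint, DLT rule or analysis population is touched.

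Most of this stands. The intent was almost certainly *and*, and the error is one of wording, not a deliberate design decision. Testing and withdrawal do reduce the harm.

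It does not dispose of the point. Section 8.2 makes these criteria the entry test, section 5.7 requires the protocol's instructions to be followed exactly, and section 10.4.1 directs monitoring at adherence to them. Enrolling a WOCBP without contraception would not breach the text, so a monitor would have no clear ground for recording a deviation.

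One limit should be stated. The SAP (section 1) plans to treat 25 patients with triple-negative breast cancer at the MTD, but this protocol contains no such cohort. The eligibility text for it is not available, so the finding cannot be extended to those patients.

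**Conclusion.** The concern holds. As written, in both places, a woman of childbearing potential who is neither pregnant nor breastfeeding and who uses no contraception is eligible. This is so under either reading of the sentence.

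Its reach is every WOCBP screened under this protocol, because the criterion rejects none of them for lack of contraception. How many would be enrolled differently cannot be stated: the documents do not give the number of WOCBP, and sites may well have applied the intended rule. No harm is shown.

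The conclusion rests on the wording alone and on the absence of a general contraception requirement elsewhere in the two documents. A later protocol version may exist, since the SAP describes a cohort that this one lacks. Whether it corrects the criterion cannot be seen. The correction should be made for patient safety; it does not affect the statistical analysis.

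**What to change.** In section 8.2.1 and in the synopsis, replace the *or* that precedes the listed conditions in criterion 9 with *and*. The criterion then requires that she is not pregnant, is not breastfeeding, and meets at least one of the two conditions. Leave the OR between the two conditions as it is. No change to criterion 10, exclusion 4 or Appendix I is needed.

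The edit is one word in two places, but it needs a protocol amendment. Section 5.7 requires written approval by all signatories and, if the change counts as substantial because it is likely to affect patient safety, approval by the ethics committees and competent authorities before implementation. It can go in with any other amendment.

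If a later version exists, check that it carries the corrected wording, including for the breast cancer cohort. For women already enrolled, confirm that agreement to contraception was documented for each WOCBP. That is a review of existing records, not new data collection.

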8.2.2 Exclusion criteria

Patients will not be eligible to participate to the study if they meet ANY of the following exclusion criteria:

1. Central nervous system involvement (excluding treated stable cerebral metastasis, not requiring therapy to control symptoms in the last 60 days).
2. Acute infection requiring IV antibiotics, antivirals, or antifungals within 14 days prior to the initiation of treatment (oral treatment are allowed).
3. Grade ≥ 2 peripheral neuropathy.
4. Pregnant or breastfeeding women.
5. Life-threatening illnesses other than solid tumors and NHL, uncontrolled medical conditions or organ system dysfunction which, in the Investigator's opinion, could compromise the patient's safety, or put the study outcomes at risk.
6. Any chemotherapy, radiotherapy, immunotherapy, major surgery, biologic, investigational or hormonal therapy for treatment of solid tumors or lymphoma within 28 days of the first administration of study treatment.
7. Less than 2 previous cancer treatments, including high-dose chemotherapy and ASCT, for NHL unless patient refuses standard therapy and/or is not eligible for ASCT.
8. Known history of human immunodeficiency virus (HIV) or active infection with hepatitis C virus (HCV) or hepatitis B virus (HBV).
9. Have an active or chronic corneal disorder or Sjogren's syndrome.
10. Have any ongoing acute inflammatory skin disease or chronic skin disease not controlled by specific treatment.
11. Have been diagnosed with another primary malignancy, except for: adequately treated non-melanoma skin cancer or cervical cancer in situ; definitively treated non-metastatic prostate cancer; or patients with another primary malignancy who are definitively relapse-free with at least 3 years elapsed since the diagnosis of the other primary malignancy.
12. Have significant, uncontrolled, or active cardiovascular disease, specifically including, but not restricted to:
 - Myocardial infarction (MI) within 6 months prior to the first dose of study drug.
 - Unstable angina within 6 months prior to first dose of study drug.
 - Congestive Heart Failure (CHF) NYHA Class III-IV
 - Diagnosis of short or long QT syndrome.
 - History of clinically significant atrial arrhythmia (including clinically significant bradycardia), as determined by the treating physician.
 - Any history of ventricular arrhythmia.

- Cerebrovascular accident or transient ischemic attack within 6 months prior to first dose of study drug.

13. Patients known to be hypersensitive to MEN1309 or to any components of the formulation.

8.2.3 Withdrawal of patients from study or discontinuation of study drug

Participation in the study is strictly voluntary and patients have the right to withdraw from the study at any time without explanation. This will not affect their rights for future medical care.

Patients may also be discontinued from study drug at the Investigator's discretion or at specific Sponsor's request at any time. Patients will be withdrawn from the study if they experience:

- Protocol violation (e.g., prohibited medication, poor compliance with study procedures/treatment).
- Disease progression.
- DLT at Cycle 1.
- Occurrence of any of the ADR criteria qualifying for DLT at any Cycle following Cycle 1.
- Life threatening related Serious Adverse Event (SAE).
- Patient receives other treatment for solid tumors or lymphoma.
- Occurrence of pregnancy.
- Patient's request.

NOTE: Patients who experienced DLT might be allowed to continue on study at a lower dose if considered beneficial by the investigator and after approval by the Sponsor.

All patients shall undergo the End of Study Visit at the time of study withdrawal or discontinuation of study drug. Unscheduled assessments showing disease progression and leading to patient's withdrawal can replace the End of Study Visit provided that all assessment/procedures scheduled for this visit are completed.

If a patient prematurely terminates the study as per patient's request, data already collected will be used and analyzed for the purpose of the study, as per local regulation.

In case of withdrawal of consent, the patient may choose if samples/images which are already collected but not analysed yet, can be analysed or shall be destroyed.

During escalation phase, patients not evaluable per DLT will be replaced.

8.2.4 End of Study

After the End of Study Visit, all patients evaluable for efficacy will be followed for survival status according to local practice (a visit or a telephone call) every 12 weeks up to a period of 12 months after first treatment administration to the last patient.

The study ends 12 months after first treatment administration to the last patient.

All biological samples (including tumor slides and block and excepting safety blood samples) collected along the study will be stored for a maximum of 10 years from the date of the last patient last visit. After 10 years, the samples will be destroyed, or a new IEC/IRB approval and informed consent will be requested to keep the samples for an additional time period.

8.3 IDENTITY OF THE INVESTIGATIONAL PRODUCT(S)

8.3.1 Description of Investigational Medicinal Product(s)

MEN1309 drug product is a concentrate for solution for infusion provided as single-use glass vials. Each vial contains 10 mL of a sterile filtered solution, with a concentration of 5.0 mg/mL MEN1309. The closure system is a rubber stopper and aluminum crimp seal with flip-off top.

Table 2: Composition of MEN1309 drug product

| Component | Quantity / container | Grade | Function |
|--|---|------------------------|--|
| MEN1309 | 5.0 mg/mL | Internal Specification | API |
| L- Histidine hydrochloride monohydrate | 10 mM Histidine (prepared from 1.610 mg/mL L-Histidine hydrochloride monohydrate and 0.360 mg/mL L-Histidine) | Ph. Eur. | buffering agent* |
| L- Histidine | | Ph. Eur., USP | buffering agent* |
| Sucrose | 50 mg/mL | Ph. Eur., USP/NF | protein stabilizer, isotonic adjusting agent |
| Glycine | 130 mM (prepared from 9.759 mg/mL Glycine) | Ph. Eur., USP | protein stabilizer, isotonic adjusting agent |
| Polysorbate 80, super refined | 0.1 mg/mL | Ph. Eur., USP/NF | surfactant |
| Water for injections | add 10 mL | Ph. Eur., USP | solvent |

* The target pH value of drug product is 5.5.

The storage declarations are: “Store at (2 – 8)°C!” and “Do not freeze!”. Additionally, the storage declaration “Keep in the outer carton!” will be applied as a matter of precaution.

For drug product administration, the required volume of MEN1309 (5.0 mg/mL) concentrate for solution for infusion will be withdrawn from the vials and diluted in 250 mL sterile 0.9 % sodium chloride solution. For concentrations from 0.009 to 0.144 mg/mL of MEN1309, 5 mL of Water for Injections with 0.1% Polysorbate 80 are added to the MEN1309 infusion solution. Preparation must be done under controlled and appropriate aseptic conditions.

Diluted MEN1309 solution should be used immediately and administered by an IV infusion lasting 3 hours. If not used immediately, the solution for infusion must be stored strictly following the instruction provided in the IMP leaflet. The solution for infusion must be discarded thereafter.

